Protocol synopsis, Section 10.1	Text updated from:  For contact lens wearers - Spherical equivalent difference of ≤ 0.5 D between outcomes from consecutive manifest refraction outcomes performed at least 7 days apart after the contact lens wear has been stopped for the appropriate period of time as follows.	Text updated to:  For contact lens wearers - Spherical equivalent difference of ≤ 0.5 D between outcomes from consecutive optical infinity adjusted manifest refraction outcomes performed at least 7 days apart after the contact lens wear has been stopped for the appropriate period of time as follows.	To emphasize that the inclusion criterion is based on the optical infinity adjusted refraction.
Protocol synopsis, Section 10.2	Text updated from:  Manifest refraction astigmatism that is more than 1.00 D than the topolyzer astigmatism assessed by Topolyzer Vario.	Text updated to:  Manifest refraction astigmatism that is more than 1.00 D than the topolyzer astigmatism assessed by Contoura software.	The data from the Topolyzer Vario is used to derive the data provided by the Contoura Software, but data from the Contoura software is more relevant to this criterion.
	1 1	Contoura software.	software is mor relevant to this

Document: TDOC-0052425 Version: 2.0; Most-Recent; Effective; CURRENT

Status: Effective Page 24 of 81

Sections	Revisions	Rationale
-		
-		

Document: TDOC-0052425 Version: 2.0; Most-Recent; Effective; CURRENT

Status: Effective Page 25 of 81

Document: TDOC-0052425 Version: 2.0; Most-Recent; Effective; CURRENT

Status: Effective Page 26 of 81

Sections	Revisions	Rationale
		_
		_
		-

Document: TDOC-0052425 Version: 2.0; Most-Recent; Effective; CURRENT

Status: Effective Page 27 of 81

Sections	Revisions		Rationale
Protocol synopsis, Section 8.5.2	Text updated from:  Mean intraocular pressure (IOP).	Text updated to::  Mean intraocular pressure (IOP) at Screening, 1 month, 3 months, and 12 months.	To specify the relevant time points.
Protocol synopsis, Section 8.5.2	Below text was deleted:  Frequency of slit lamp Frequency of dilated f		Deleted as no descriptive statistics will be performed for either assessment, only listings provided.
Protocol synopsis, Section 8.5.2	Text updated from: Frequency of adverse events.	Text updated to:  Frequency of treatment- emergent adverse events.	To clarify that the analysis will be around AEs which occur after surgery.

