### 12.1.3 Post-Surgery follow-up Visits (Day 1, Week 1, Months 1, 3 and 12)

Below is a list of study procedures to be undertaken at the Post-Surgery follow-up Visits (Day 1, Week 1 [Day 5 to Day 9], Months 1 [Day 21 to Day 35], 3 [Day 70 to Day 98] and 12

Effective Date: 19-Mar-2017 Page 58 of 81 Alcon - Business Use Only Protocol - Clinical

Version: 2.0; Most-Recent; Effective; CURRENT Document: TDOC-0052425

Status: Effective

[Day 330 to Day 375]). Procedures must be performed in the order presented below unless otherwise stated. All ocular assessments must be done monocularly.

- 1. Record any changes to subjects' ocular and non-ocular medical history or concomitant medications at all visits.
- 2. Administer the RSVP Questionnaire at the Month 1, 3, and 12 visits.
- 3. Administer the SQDES Questionnaire at the Month 1, 3, and 12 visits.

NOTE: Investigators and site staff must review both questionnaires results prior to subjects leaving the office to ensure completeness.

- 4. Conduct the following procedures in an order that is feasible for your site:
  - Perform lighting measurements for VA and contrast sensitivity testing at all visits.
  - Measure distance UCVA in photopic conditions at all visits.
  - Measure uncorrected contrast sensitivity in mesopic conditions at the Month 1, 3, and 12 visits.
  - Measure manifest refraction at 4 meters and adjust for optical infinity at the Week 1, Month 1, 3, and 12 visits.
  - Measure distance BCVA in photopic conditions at the Week 1, Month 1, 3, and 12 visits.
- 5. Conduct the following procedures in an order that is feasible for your site:
  - Perform topography at the Month 1, 3, and 12 visits.

- 6. Perform slit lamp examination at all visits.
- 7. Measure IOP at the Month 1, 3, and 12 visits.
- 8. Perform dilated fundus examination at Month 12.
- 9. Record any AEs at all visits. Refer to Section 13 for further details.

*NOTE*: SAEs must be entered into EDC within 24 hours of the Investigator's knowledge.

*NOTE:* Secondary Surgical Intervention: Retreatments will not be allowed in this study.

Effective Date: 19-Mar-2017 Page 59 of 81 Alcon - Business Use Only Protocol - Clinical

Version: 2.0; Most-Recent; Effective; CURRENT Document: TDOC-0052425

Status: Effective

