# 13.3 Procedures for Recording and Reporting

AEs are collected from the time of informed consent. Any pre-existing medical conditions or signs/symptoms present in a subject prior to the start of the study (i.e., before the ICF is signed) are not considered AEs in the study and should be recorded in the Medical History section of the eCRF.

In addition, corneal edema and superficial punctate keratitis are examples of early post-operative findings that are typically observed following ocular refractive surgery. These

Print Date: Print Date:

Alcon - Business Use Only Protocol - Clinical Effective Date: 19-Mar-2017
Page 64 of 81

Document: TDOC-0052425 Version: 2.0; Most-Recent; Effective; CURRENT

Status: Effective

are not considered AEs if they can be reasonably expected to resolve within a week and not result in any untoward long term visual outcome impact.

For each recorded event, the ADEs and SAEs documentation must include: date of occurrence, severity, treatment (if applicable), outcome, and assessments of the seriousness and causality. In addition, the Investigator must document all device deficiencies reported or observed with the Wavelight EX 500 Laser system and the VisuMax Laser keratome system on the Device Deficiency eCRF. The site must submit all available information on ADEs, SAEs, and device deficiencies to the Study Sponsor immediately as follows:

- All SAEs must be reported immediately (within 24 hours) of the Investigator's or site's awareness.
- ADEs that do not meet seriousness criteria and device deficiencies must be reported within 10 calendar days of the Investigator's or site's awareness.
- A printed copy of the completed Serious Adverse Event and Adverse Device Effect and/or Device Deficiency eCRF must be included with product returns (refer to Section 11.3 Accountability Procedures).
- Additional relevant information after initial reporting must be entered into the eCRF as soon as the data become available.
- Document any changes to concomitant medications on the appropriate eCRFs.
- Document all relevant information from Discharge Summary, Autopsy Report,
   Certificate of Death etc., if applicable, in narrative section of the Adverse Device
   Effect (for related AEs) and Serious Adverse Event eCRF.

NOTE: In the case of the EDC system becoming non-operational, the site must complete the			
appropriate paper Serious Adverse Event and Adverse Device Effect and/or Device			

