### 15 ANALYSIS PLAN

The main focus of the analyses is the eye (individual-level) rather than subject (group-level). However some data (e.g. demographics, non-ocular AEs) will only be available at the subject level.

At each study visit, quantitative variables will be presented based on descriptive statistics (the number of non-missing observations, mean, median, standard deviation [SD], minimum and maximum values) for the observed values and change from pre-surgery (if applicable). Qualitative variables will be presented by frequency tables.

The baseline value is the last available, non-missing, value collected prior to surgery (i.e. prior to the laser being in contact with the eye).

Further technical details and discussion of the following statistical considerations will be provided in the statistical analysis plan (SAP), which will be finalized before DBL.

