### **Other Safety Assessments**

Other safety evaluations include slit lamp findings IOP, surgical problems, dilated fundus findings and PRO Questionnaires (RSVP, SQDES). For details refer to Section 12.1.

The mean overall and eight subscale vision related quality scores will be derived from the RSVP questionnaire.

For SQDES, a subject is defined as having dry eye syndrome if there was occurrence of both dryness and irritation of the eyes either constantly or often (that is, severe symptoms) or a report of a previous clinical diagnosis of dry eye syndrome.

Information from the nomogram, if one is used, and surgical report will also be provided.

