6.3.3 Biomicroscopy Findings/Slit Lamp Examination

A listing will be provided which presents all eyes with an abnormality in any slit-lamp parameter at any post-surgery visit. The listing will include the following variables: surgery group, investigator, subject, age, sex, race, ethnicity, visit, eye, parameter, baseline value and value at the visit. "Other" slit lamp examination findings will be listed along with their MedDRA dictionary (Version 19.0 or a more recent version) primary SOC and PT codes.

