6.3.5 Dilated Fundus Examination

A listing will be provided which presents all eyes with an abnormality in any fundus parameter at any post-surgery visit. The listing will include the following variables: surgery group, investigator, subject, age, sex, race, ethnicity, visit, eye, baseline value, and value at the visit.

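### Slit-lamp and dilated-fundus findings are listed but not tabulated, so findings not reported as adverse events have no count or rate by arm

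*Protocol*

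**What the plan says.** **Examinations.** Protocol 12.1.3 covers Day 1, Week 1 and Months 1, 3 and 12. It says "Perform slit lamp examination at all visits" and "Perform dilated fundus examination at Month 12". The slit lamp is therefore scheduled five times after surgery and the fundus once.

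**Protocol on outputs.** The opening of Section 15 states "Qualitative variables will be presented by frequency tables". Section 15.7, under Other Safety Assessments, reads "Other safety evaluations include slit lamp findings IOP, surgical problems, dilated fundus findings and PRO Questionnaires (RSVP, SQDES". Neither place says that the two examinations are exempt from tabulation. Neither appears among the safety endpoints in Protocol 8.5.2 or SAP 6.1. The log in Protocol 5.1 gives the reason for taking the two frequencies out of 8.5.2: "Deleted as no descriptive statistics will be performed for either assessment, only listings provided".

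**SAP on outputs.** Section 6.3.3 says "A listing will be provided which presents all eyes with an abnormality in any slit-lamp parameter at any post-surgery visit". Section 6.3.5 says "A listing will be provided which presents all eyes with an abnormality in any fundus parameter at any post-surgery visit". Neither section plans a table.

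**Adverse event route.** Protocol 13.2 makes an untoward change in a study parameter an adverse event when the investigator considers it clinically relevant. Section 13.3 says that "corneal edema and superficial punctate keratitis are examples of early post-operative findings". It excludes such findings if they should clear within a week and have no lasting effect on vision.

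**The concern.** The trial compares two corneal procedures, and the slit lamp is the routine means of seeing what each does to the cornea. Protocol 9.3.1 says the risks of SMILE are still under investigation. It names haze, dry surface, epithelial islands, infiltrates and interface inflammation among the reported postoperative complications, and flap complications for LASIK.

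A listing of abnormal eyes gives no denominator. A reader who wants to know what share of eyes in each arm had a given finding at Week 1 would have to count rows by hand and find the number examined elsewhere. For findings that never become adverse events, no other planned output supplies the answer. At stake is the completeness of the descriptive safety comparison, not any hypothesis test.

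**Working it through.** The plan gives no figure on this point, so the check is mainly a comparison of provisions.

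**Step 1. What each item named in Protocol 15.7 receives in the SAP.**

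| Item | SAP section | Output by surgery group |
|---|---|---|
| IOP | 6.3.4 | Descriptive statistics, plus listing |
| Surgical problems | 6.3.8 | Counts and percentages of eyes, plus listing |
| RSVP | 6.3.7 | Descriptive statistics |
| SQDES | 6.3.7 | Frequency table and shift table |
| Slit lamp | 6.3.3 | Listing of abnormal eyes only |
| Dilated fundus | 6.3.5 | Listing of abnormal eyes only |

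Only the last two lack a summary.

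**Step 2. What the adverse event tables recover.** SAP 6.3.1 tabulates ocular treatment-emergent events, ocular serious events, adverse device effects and serious adverse device effects. It does so by surgery group, system organ class and preferred term, with subject counts, percentages and event counts. Protocol 13.1 makes a named set of events serious by rule:
- moderate or worse diffuse lamellar keratitis;
- infiltrate or ulcer;
- epithelial defect persisting at one month or later;
- moderate or severe edema at one month or later;
- flap melting;
- loss of two or more lines of BCVA;
- retinal detachment;
- perforation.

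All of these are counted by arm.

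**Step 3. What remains.**
- Findings judged not clinically relevant under 13.2. The masking provisions (Protocol 7.2 and 13.5, SAP 1.4) cover only those who perform refraction and UCVA testing, so this judgement may be made with the arm known. Slit-lamp examiners need not be masked either, so a table would remove only the second layer of judgement.
- Early edema, punctate keratitis and similar findings that meet both conditions in 13.3.
- Rates per eye examined and per visit for any finding. The adverse event tables count subjects and events over the whole period from surgery to Month 12.

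**Step 4. Volume.** Protocol 15.9 expects 200 subjects per arm treated in both eyes, which is 200 × 2 = 400 eyes. Slit lamp: 400 × 5 = 2,000 scheduled post-surgery examinations per arm. Fundus: 400 × 1 = 400. Both figures are before dropout.

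**Step 5. Would a table be informative? (Illustration only.)** The plan's sample size reproduces. For 90% vs 80%, two-sided 5% and 90% power, 266 independent eyes per arm are needed, and 266 × (1 + 0.39) / 2 = 184.9, against the stated 185. The documents give no finding rates and no between-eye correlation for findings. Assume 5% of eyes in each arm and a correlation between 0 and 1. Then effective eyes = 400 / (1 + ICC), and the 95% half-width for the arm difference = 1.96 × √(2 × 0.05 × 0.95 / effective eyes).

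| ICC (assumed) | Effective eyes | Half-width |
|---|---|---|
| 0 | 400 | 3.0 points |
| 0.39 | 287.8 | 3.6 points |
| 1 | 200 | 4.3 points |

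A descriptive table would therefore carry usable information. The conclusion does not rest on these widths.

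**The case against.** The strongest reply is that the events that matter most are already counted. Infiltrates are serious by rule. Intraoperative flap problems fall under surgical problems, which are tabulated by eye. Dry-eye symptoms have a frequency and a shift table (SAP 6.3.7), and BCVA change is tabulated by category (SAP 6.3.2). Haze or interface inflammation enters the adverse event tables once judged clinically relevant. The sentence in Section 15 is generic, and that section leaves technical detail to the SAP. Section 15.7 names the examinations without promising a table. The listings carry surgery group, baseline value and visit value, so affected eyes can be identified by arm. No safety inference is planned.

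Most of this stands, and it confines the point to a narrow residue. It does not supply a count by arm for findings outside adverse event reporting, or a denominator for any finding.

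Three stronger readings are tempting and should be resisted.
- A reader might infer that corneal and retinal findings are never counted by arm. SAP 6.3.1 and 6.3.8 show otherwise.
- A reader might infer that Amendment 1 removed an analysis and the SAP then followed. The SAP is effective 19-Dec-2016, is based on protocol 1.0 and already planned listings only. Protocol 2.0, effective 19-Mar-2017, came later and moved toward it. The log entry is not itself an error.
- A reader might infer that every eye is examined throughout. A second eye left untreated, or given non-study surgery, contributes adverse events only (Protocol 12.1.2 and 15.7), and the scheduled post-surgery fundus examination is at Month 12 alone.

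**Conclusion.** The point holds in limited form. SAP 6.3.3 and 6.3.5 do not match the general rule in Protocol Section 15, and no stated exemption reconciles them. The rationale in the amendment log restates the decision without justifying it. The consequence is that slit-lamp and fundus findings not reported as adverse events have no planned count or percentage by arm, and no finding has a rate per eye examined at each visit. About 2,000 scheduled slit-lamp and 400 fundus examinations per arm are affected, assuming 400 treated eyes and no dropout. How many would show a finding outside the adverse event tables cannot be derived from the documents.

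This is a gap in descriptive safety reporting. It leaves the primary test, alpha, multiplicity procedure, sample size and data collection untouched. It is worth correcting because the correction is cheap.

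**What to change.** - In SAP 6.3.3, add a descriptive table by arm and visit: number of treated eyes with each slit-lamp abnormality over number of treated eyes examined, and the number with that abnormality absent at baseline.
- In SAP 6.3.5, add the same table for fundus findings at Month 12.
- Keep both listings.
- Bring Protocol 8.5.2, the synopsis and Section 15 into line with these outputs.

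If the sponsor prefers listings only, a sentence in Section 15 exempting the two examinations would remove the inconsistency but leave the reporting gap.

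The cost is two tables programmed from data already collected, some wording changes and a slightly longer safety report. No additional examination or subject is needed. The slit-lamp table through Month 3 can accompany the main analysis, and the fundus table belongs with the final one.

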# Version: 2.0; Most-Recent; Effective; CURRENT

### **SCHEDULE OF VISITS** 6

6 SCHEDULE OF VISITS  Table 6–1 Schedule of Assessments    Level   Pre-surgery   Surgery h   Post-Surgery   UNSV j									
Table 6–1	Schedule o	f Assessments							
	Level	Pre-surgery	Surgeryh	Post-Surgery					UNSV j
Procedure	Subject/Eye	Screening (Day -45 to Day -1)	Day 0ª	Day 1	Week 1 (Day 5 to Day 9)	Month 1 (Day 21 to Day 35)	Month 3 (Day 70 to Day 98)	Month 12 k (Day 330 to Day 375)	N/A
Informed consent b	S	X							
Demographics	S	X							
Medical/ocular history/concomitant medications	S/E	X	X	X	X	X	X	X	X
Inclusion/exclusion criteria	S/E	X	X						
Pregnancy test c, f	S	X							
RSVP questionnaire f	S	X				X	X	X	
SQDES f	S	X				X	X	X	
Photopic Distance UCVA e, f	Е	X		X	X	X	X	X	X
Mesopic Uncorrected contrast sensitivity f	Е	X				X	X	X	
Manifest refraction f	Е	X			X	X	X	X	X
Photopic Distance BCVA e, f	Е	X			X	X	X	X	
Pupillometry f	Е	X							
Keratometry d, f	Е	X							
Topography d, f	Е	X				X	X	X	
Pachymetry f	Е	X							
Axial length f	Е	X							
Slit lamp examination f	Е	X	X	X	X	X	X	X	X
IOP f	Е	X				X	X	X	X
Cycloplegic refraction	Е	X							

Month 12k

(Day 330 to Day

375)

X

X

UNSVj

N/A

Χ

Χ

Print Date:

Status: Effective

Surgeryh **Post-Surgery** Subject/Eye Screening Week 1 Month 1 Month 3 Procedure Day 0a (Day -45 to Day 1 (Day 5 to Day (Day 21 to (Day 70 to Day Day 35) Day -1) Dilated fundus Ε X examination Randomizationg S X LASIK or SMILE Ε Χ X S/E X Χ Χ Χ X Adverse events Χ Device deficiencies NA Χ Problems during surgery S/E

X

Pre-surgery

- a. Relevant measurements from the Pre Surgery Visit should be repeated prior to surgery if needed to provide accurate Baseline measurements pre-surgery. This includes the second optical infinity adjusted manifest refraction to demonstrate refractive stability in contact lens wearers as outlined in Inclusion Criteria 9.
- b. All subjects must consent to bilateral treatment; both eyes are to be treated on the day of surgery.
- c. Women of child-bearing potential only.

Other procedures during

surgery

d. Keratometry and corneal topography must be done prior to IOP and pachymetry.

S/E

Level

- e. Distance UCVA and BCVA will be measured at each visit using an ETDRS chart at 3 meters (10 feet) or 4 meters (13 feet). For subjects who cannot read English letters, a numerical, Tumbling E or a Landolt C logMAR chart can be used.
- f. These tests must be done prior to the instillation of dilating or cylcoplegic agents.
- g. Randomization must be completed following all screening procedures and confirmation of subject eligibility during the Pre-Surgery visit.
- h. Surgery must occur within 45 calendar days from the Pre Surgery Visit. Pre Surgery Visit and Surgery Visit cannot occur on the same day.
- i. AEs should be collected from time of consent.
- i. At an unscheduled visit, safety assessments and other assessments needed as per investigator's discretion may be performed.
- k. If a subject discontinues early, these procedures should be performed before exiting the subject. Month 12 (Final Visit) procedures should be performed at the last available visit, if at all possible.
- 1. Includes intraoperative complications.

RSVP=Refractive Status and Vision Profile, SQDES=short questionnaire for dry eye syndrome, UCVA=uncorrected visual acuity, BCVA=best corrective visual acuity, IOP=intraocular pressure, LASIK=Laser in situ keratomileusis, SMILE=Small incision lenticule extraction, ETDRS=Early Treatment Diabetic Retinopathy Study, LogMAR=Logarithm of the Minimum Angle of Resolution, UNSV= unscheduled visit.

Document: TDOC-0052425 Version: 2.0; Most-Recent; Effective; CURRENT

Status: Effective

### 7 INTRODUCTION

### 7.1 Background

Laser in situ keratomileusis (LASIK), a refractive surgery procedure, has been in use for over 20 years for the correction of refractive error. The refractive error correction is achieved by the ablation of the required amount of corneal stromal tissue by an excimer laser. The WaveLight® EX500 excimer laser system is the most recent Alcon excimer laser (Sugar 2002).

Treatment planning for LASIK is done with the refractive error correction data and with or without other patient specific pre-surgical data. The use of patient specific pre-surgical data offers customization of LASIK. For example, with Topography Guided LASIK, corneal height data is used to plan the LASIK surgery. Topography Guided LASIK has been available outside the US since 2003 and had been used primarily for the treatment of irregular or diseased corneas that either had never been treated or had been previously treated (Knorz 2000, Kymionis 2004, Holland 2013). More recently, Topography Guided LASIK is being used as a primary treatment for regular corneas. A study by Stulting et. al showed that Topography Guided LASIK as a primary treatment for myopia with or without astigmatism was safe and effective in subjects who had regular corneas (Stulting 2016).

Small incision lenticular extraction (SMILE) is the newest refractive surgery procedure that is being used for the correction of myopia with or without astigmatism. The Zeiss VisuMax laser keratome ophthalmic surgical laser, a femtosecond laser, is the only marketed laser for the SMILE procedure. The VisuMax creates a lenticule of corneal tissue and a small (<4mm) channel through which the lenticule is removed. The removal of the lenticule results in correction of the refractive error. Refractive error correction data but not corneal height data is used in the treatment planning of SMILE. Data in the literature for SMILE is showing good outcomes for safety and effectiveness (Ivarsen 2014, Moshirfar 2015).

Fundamental difference between the EX500 and VisuMax are that the EX500 provides centration and cyclotorsion control, and the VisuMax does not. Centration and cyclotorsion control allow for better correction of astigmatism. Additionally, use of the topography data for treatment planning of Topography Guided data should allow for better correction of astigmatism compared to SMILE for which topography data is not used for treatment planning.

Myopia with astigmatism is a common refractive error (MarketScope 2015), and this study is designed to determine if the Topography Guided LASIK with the EX500 is superior to

**Document:** TDOC-0052425

Version: 2.0; Most-Recent; Effective; CURRENT

Status: Effective

SMILE with the VisuMax for the correction of astigmatism in subjects with myopia and astigmatism.

